1.0 LIST OF ABBREVIATIONS/GLOSSARY OF TERMS

AE	Adverse Event
AnMach	Anaesthetic Machines
CI	Chief Investigator
COVID19 or COVID-19	Coronavirus Infectious Disease 2019
CRF	Case Report Form
GCP	Good Clinical Practice
HRA	Health Research Authority
ICF	Informed Consent Form
ISF	Investigator Site File
ITU	Intensive Therapy Unit
MHRA	Medicines and Healthcare Products Regulatory Agency
NHS R&D	National Health Service Research & Development
PIS	Participant Information Sheet
QA	Quality Assurance
QC	Quality Control
REC	Research Ethics Committee
RFL	Royal Free London
SDV	Source Document Verification
SOP	Standard Operating Procedure
SSA	Site Specific Assessment

3.0 STUDY SUMMARY

Official title:	Evaluation of the impact of using anaesthetic machines for ventilation on COVID-19 patients and professionals. A mixed methods study.
Brief title /Acronym:	COVID19 AnMach
Sponsor reference number:	133491
Study Population/disease condition	Phase 1. Patients ventilated on anaesthetic machines during COVID-19 surge in April and May 2020. Phase 2. Professionals who managed patients on an anaesthetic machines on the above-mentioned period.
Research Question	What is the impact of ventilating patients on an anaesthetic machine?
Study design	Observational non-interventional retrospective data collection, survey and qualitative study
Eligibility criteria:	
Inclusion criteria:
 
Phase 1. Adult patients >18 years old admitted to RFH ITU from the 1st of April 2020 until the 30th of October 2020; ventilated with an anaesthetic machine during their ITU admission.
 
Phase 2. ITU professionals who managed patients ventilated using anaesthetic machines at the RFH ITU between the same period.
 
Exclusion criteria:
 
Phase 1. Patients ventilated with ITU grade ventilators from admission.
 
Phase 2. Professionals who did not managed patients on an anaesthetic machine.

Anticipated start date	01/07/2020
Anticipated end date	30/11/2020
Target number of subject's/data sets	Maximum 15 patients related datasets
Target number of participants	Maximum 20 professionals' interviews
Primary aim	The study aims to identify issues with ventilation of COVID-19 positive critically ill patients on anaesthetic machines that are not described in available guidelines.

	Adverse events affecting patient's management and the staff experience of using anaesthetic machines are explored.
Sources of funding	Royal Free Charity
Sponsor	Royal Free London NHS Foundation Trust
Contact name	Sponsor representative : [name] Email: [contact] [contact] Fax : NA Chief Investigator: [name] Email: [contact] [contact] Fax: N/A

4.0 STUDY FLOW CHART

5.0 INTRODUCTION

5.1 BACKGROUND

The COVID-19 pandemic dramatically increased the demand for the ventilator beds in the United Kingdom (UK), generating, at the same time, Intensive Therapy Unit (ITU) ventilators shortages (Lauer et al., 2020). Anaesthetic machines (AnMach) have been commonly used as a solution to supplement ventilator capacity. The use of AnMach as a long-term ventilator is considered an off-label use but emergency use of these devices is justified when there is no available alternative because the benefits outweigh the risks (Government UK, 2020; Food and Drug Administration Staff 2020). This occurred at the Royal Free Hospital (RFH), London, in April and May 2020.

Modern AnMach are capable of providing mechanical ventilation to patients with respiratory failure, however they neither are ITU grade ventilators nor their use as such has been verified and validated

(GE Healthcare, 2020). Safe and effective use of AnMach as ventilators requires understanding of the differences between AnMach and ITU ventilators and their limitations in mimicking ventilation strategies (APSF/ASA, 2020).

Both machines provide air and oxygen from a wall to patients at desired ventilation settings and oxygen concentration. The AnMach have a rebreathing system where the expired air goes through a filter (soda lime, that has a limited capacity of absorption and needs replacing) that catches the carbon dioxide and the “cleaned” air goes back to the patient. To do this they need high flow volume, more than 50% of the patients’ minute volume (air volume given to patients each minute). The ITU ventilators are non-rebreathing systems so exhaled breath is dispersed to the atmosphere and a new air mix is given to patients at every breath. AnMach are designed to be full time attended because they have limited ability to generate alerts. Also, they may contain residual anaesthetic gas in the system that could interact with other patients’ medication. AnMach need testing every 24hours and need to be set ready to ventilate while ITU ventilators are ready to go as soon as the patient is connected (GE Healthcare, 2020).

Although regulatory authorities approved the emergency use of AnMach as ventilators, it has been stated that healthcare professionals using these machines must be appropriately trained (Government UK, 2020; Food and Drug Administration Staff 2020). Similar statements have been issued by the manufacturers (Lauer et al. 2020; GE Healthcare, 2020; Getinge, 2020). To outline the potential risks related to the use of AnMach as ventilators, the UK MHRA issued a Medical Device Alert in early April 2020 highlighting the actions required to minimise hazards (Government UK, 2020). At the end of April 2020, NHS England and NHS Innovation published a new comprehensive clinical guidelines for use of AnMach to provide continuous invasive ventilatory support for adult patients during the coronavirus pandemic. The guidelines were long awaited and launched when the UK passed the surge. The guidelines described the major differences between AnMach and ITU ventilators as well as highlighted potential issues with ventilation using AnMach and provided advice how to deal with them (NHS England, 2020). It has been recommended that anaesthetic machines should be used in patients with the lowest critical care acuity scores and relatively good lung compliance. The guidelines also acknowledge that if a patient’s lung compliance (the extent to which the lungs will expand) deteriorates it may be necessary to transfer a patient on to ITU grade ventilator.

The most common issues with ventilating patients on AnMach, according to the NHS England guidance, are (NHS England, 2020):

1. Problems with altering the fresh gas flows (FGF) and the degree of rebreathing: the FGF should be set to avoid rebreathing and generation of excess humidity. Moreover, the amount of oxygen given to the patients depends on the FGF and the amount of rebreathing. An increase in FGF every 4 hours is recommended to help dry the internal components of the machine.
2. Need of changing soda lime for absorption of CO₂: the risk of CO₂ rebreathing occurs in case of exhaustion of soda lime activity.
3. Potential to deliver hypoxic mixture at low flows: low flows are not recommended for long term ventilation of ITU patients.

4. Absence of a pressure relief valve to limit the maximum pressure of the air flow given to the patients that put the receiver at increased risk of barotrauma.
5. Increasing resistance to gas flow due to saturation of filters with water: water vapour is produced by CO₂ absorbers. If the water is not expelled, monitors may indicate easily overlooked flow tracing errors (prolonged expiratory phase, slurring of the expiratory capnography) and increased airway pressure may occur. Periodic drainage of water from the circuit is required which may result in an alternative means of ventilation being used.
6. Collection of water in dependent areas (part of tubes where water sits lower by gravity) of the breathing system: pressure/flow oscillations may be sensed by the ventilator as patient inspiratory effort which in turn will make a total respiratory rate greater than the set one and have a detrimental effect on patient's ventilation.
7. Lack of leak compensation in case of a leak of air flow: this may result in loss of inspiratory pressure and end-expiratory pressure and falling of the bellows (the bag where air flow goes in to be subsequently pushed into patient's lungs) resulting in inadequate ventilation. Several strategies need to be employed including manual ventilation during suctioning of secretions.
8. A 'backup mode' of ventilation is not always present: the lack of the apnea mode (if patients doesn't breathe the system starts ventilating for him) may result in prolonged apnea if patient loses respiratory drive while on spontaneous mode of ventilation.

During the pandemic, the rapid deployment and repurposing of available devices were not the only actions taken to tackle care challenges. The increased demand for ITU beds also resulted in ITU staff shortages and subsequent deployment of non-ITU trained staff to help to look after ITU patients. This caused a significant change in approach to patient care, capacity management and training on ITU (Nursing and Midwifery Council, 2020) to guarantee quality of care. The guidance by the American Society of Anaesthesiologists states "Intensivists [ed. the ones that are not anaesthetists], ICU nurses and respiratory therapists are not trained to manage anaesthesia machines and are likely to be overextended and stressed" (APSF/ASA, 2020). Undoubtedly the expanding pandemic, significant and rapid change to working pattern, and the lack of experience with managing AnMach were personally and professionally challenging for both ITU staff and redeployed professionals and may have caused some of them to experience moral injury or mental health problems (Greenberg et al., 2020).

5.2 RATIONALE

In order to meet the increased demand for ITU beds, in many hospitals in the UK, and in particular at the RFH, general care wards were transformed into ITUs in preparation for the surge. The ward 2North A (2NA) and the main recovery room at the RFH has been equipped with AnMach with a view to admit COVID-19 surge ventilated patients. Patients were looked after by either anaesthetic or intensive care consultants as well as ITU and non-ITU nurses and doctors.

Evidence around the use of AnMach for long-term ventilation and weaning of critically ill patients is scarce. Published studies are dated and based on test lung model and compare the performance of the AnMach and ICU ventilators in the laboratory settings (Jaber et al., 2006; Tung et al., 2005). Despite recently disseminated guidelines, professionals who managed surge patients admitted to 2NA/main recovery may have not been familiar with the equipment and not been aware of the newly published evidence.

This study aims to explore the clinical outcome of patients admitted to 2NA/main recovery in April and May 2020, identify possible adverse events related to the use of AnMach as ventilators, and capture the experience of staff using unfamiliar equipment and managing non typical cases. The results of our study will potentially allow us to identify additional risks of using AnMach as ITU ventilators rather than the ones published in the guidelines and to recognise hidden areas for improvement of care and staff support to address.

6.0 RESEARCH QUESTION

What is the impact of ventilating patients on an anaesthetic machine in term of adverse events and ITU professionals experience?

6.1 PRIMARY AIM

This observational study is set to evaluate the impact of using anaesthetic machines for ventilation of COVID-19 positive ITU patients admitted to the RFH 2NA and main recovery location. The study aims to identify issues with ventilation of critically ill patients on anaesthetic machines that are not described in available guidelines. Adverse events affecting patient's management and the staff experience of using anaesthetic machines are explored.

6.2 OBJECTIVES

- To collect quantitative data from the charts of patients admitted to 2NA/main recovery from the 1stApril 2020 to the 30th October 2020.
- To survey ITU staff in order to identify professionals that manage patients ventilated via anaesthetic machines.
- To interview consenting professionals that rotated in 2NA/main recovery in the study period: 3 to 5 nurses, 3 to 5 physiotherapists, 3 to 5 doctors trained in Intensive Care, and 3 to 5 consultant physicians (ITU staff but not trained in anaesthesia).
- To perform statistical and thematic analysis of data.
- To prepare a report for HRA and the RFH Research and Development (R&D) Department, dissemination of study results to participants and appropriate stakeholders, preparing manuscript for publication into an Intensive Care/Anaesthetic journal.

7.0 TRIAL DESIGN

This is an observational mixed methods study and no additional interventions will be performed.

7.1 METHODS

This project consists of two parallel phases:

Phase 1, a quantitative, observational, cohort study to detect the effect of exposure to anaesthetic machine ventilation of COVID-19 patients in term of adverse events.

The quantitative phase may be also divided in two parts:

1a, a retrospective data collection of patients admitted to RFH ITU (and possibly the Barnet Hospital ITU) and connected to anaesthetic machines between the 1st April and 1st June 2020, and

1b, a prospective data collection of cases that occur between the 1st June and the 30th October 2020 in order to cover a new period of possible COVID-19 surge.

Phase 2, a survey and an interview stage engaging ITU professionals that managed patients on anaesthetic machines during the COVID-19 surge in an unfamiliar environment (nurses, physiotherapists, and doctors).

Mixed methods were chosen to integrate elements of quantitative and qualitative research in order to achieve a broader understanding of the topic. Also using both methods and integrating results helps determining the interview phase sample and interpreting the findings of the quantitative phase (O'Cathain et al., 2007).

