9 STUDY PROCEDURES

9.1 PHASE 1 PROCEDURES: quantitative cohort study

9.1.1a - Retrospective data collection

The quantitative phase of this study aims to broadly examine the impact of using anaesthetic machines for ventilation of COVID-19 positive patients.

Important note: current inability to access the patient notes and observation charts (access to notes is requiring a quarantine period once a patient has been discharged from ITU; this is currently 2 weeks) may lead to partial availability of the data described in the endpoints section. Anecdotal evidence from discussions with nursing staff suggests that it may not be possible to tell from the documentation which patients were ventilated with AnMach versus a conventional ITU ventilator. This issue can only be addressed following accessing some of the observation charts that have been processed and released from quarantine. At this moment we can hypothesise two options:

Option I, we can label the charts as AnMach use: It will be possible to perform a clinical outcomes and adverse events comparison between patients identified as being ventilated by AnMach and those

identified as being ventilated by conventional ICU ventilators. In this case (less likely) we will request a study amendment after having access to the chart and being sure we can achieve this. We will also request an amendment in case of a second surge of COVID19 for the prospective data collection.

Option II, we cannot distinguish which device was used to ventilate the patients: adverse events possibly linked to AnMach will be recorded from charts of all patients admitted to 2NA and main recovery between the 1st April and the 1st of June 2020. We will also review Datix database for any serious incidents related to the use of AnMach.

The remaining sections refer to this option II = we cannot label charts as AnMach (more likely to be the case).

The Methods for Phase 1 of this study can be broken down into the following sections:

1. Identification of study participants:

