Prospective data may be suitable for collection depending on the course of the COVID-19 crisis. At present there are no patients at the Royal Free Hospital being ventilated on anaesthetic machines. However, if there is a 'second surge' in cases and the department is forced to re-expand and use anaesthetic machines for ventilation then there may be scope to develop a prospective element to data collection. Should there be patients being ventilated with anaesthetic machines in the future, we would consider a prospective cohort study to examine outcomes for patients ventilated by anaesthetic machines and request an amendment of the study protocol to HRA.

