10 STUDY COMMENCEMENT

The study will only commence once evidence of the following approval/essential documents are in place:

1. HRA approval,
2. Final sponsorship and host site confirmation of capacity and capability.

Phase 1 and phase 2 will start in parallel. The recruitment process for **phase 2** will happen in the RFH ITU. The CI and her delegate will approach ITU professionals and ask them to do the survey on a computer or a tablet or a mobile phone. An email will be circulated to the ITU staff containing the survey link.

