11 DATA MANAGEMENT AND QUALITY ASSURANCE

Data collection points:

- Retrospective data collection: 1st of July – 30th of October 2020
- Survey: 1st of July – 31st of July 2020
- Interviews: 15 July – 31st of Sept 2020

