13.2 STATISTICAL ANALYSIS PLANS

The retrospective (and prospective, if available) data collection:

This is a cohort study with no sample size calculation. The number of patients managed on AnMach and charts available (identified as AnMach Use) will dictate how many cases we will be able to analyse. The statistical analysis will be descriptive and performed with the Microsoft Office Excel data analysis package in case we will not be able to identify the AnMach charts and we will collect only adverse events data and report them as proportions. The clinical outcomes will be described using absolute and relative frequencies (expressed as a percentage) or position indices (average or median) and relative dispersion indices (standard deviation or interquartile range) suitable for the type of variable analysed. If comparison between AnMach patients and ITU ventilator patients will be possible, mean and standard

23

deviation of clinical outcomes for the two groups will be compared (the plan for this analysis will be explained in case of requesting a protocol amendment).

The Survey:

The questionnaire answers will be inserted in an excel spreadsheet and cleaned. Incomplete, inaccurate and missing data will be detected and discussed during interviews. The results will be used to select participants for the second stage and implement the topic guide for interviewing the volunteers. For this aspect of the study the statistical analysis will be descriptive and performed with the Microsoft Office Excel data analysis package. Data will be reported as proportions.

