15.1 DEFINITION OF THE END OF TRIAL

The end of the data collection will be marked as the Last Data entry point. The end of the study is scheduled as the 30th of November 2020 providing a study commencement date on the 1st of July 2020.

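### Part 1b is labelled prospective from 1 June 2020, before the study can start; later cases have no stated case finding, and 1a and 1b are not separated in the analysis

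*Protocol*

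**What the plan says.** All references are to the protocol; the SAP, if there is one, is not at hand.

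- **Parts of Phase 1 (7.1).** Part 1a covers patients "connected to anaesthetic machines between the 1st April and 1st June 2020". The second part is "1b, a prospective data collection of cases that occur between the 1st June and the 30th October 2020".
- **Start of the study.** Section 15.1 schedules the study's end "providing a study commencement date on the 1st of July 2020". Section 10 adds: "The study will only commence once evidence of the following approval/essential documents are in place". The list that follows includes HRA approval.
- **Status of 1b (9.1.1a and 9.1.1b).** Prospective collection would be considered after a second surge, and the team would then "request an amendment of the study protocol to HRA". Section 9.1.1b also records that no patient at the hospital was on an anaesthetic machine when the text was written.
- **Case finding (9.1.1a).** Under Option II, the one thought more likely, "adverse events possibly linked to AnMach will be recorded from charts of all patients admitted to 2NA and main recovery", with dates from 1 April to 1 June and a check of the Datix incident database. The patient list is drawn for the same dates.
- **Eligibility.** The summary (3.0), the first objective (6.2) and the Phase 1 inclusion criteria (8.1.1) all run to 30 October.
- **Schedule (11).** The only entry for patient data is "Retrospective data collection: 1st of July – 30th of October 2020". The summary likewise describes the patient data as retrospective.
- **Analysis.** In 13.2 a single descriptive plan stands under "The retrospective (and prospective, if available) data collection". Section 13.1.1 gives each primary endpoint as one proportion, and 13.2.2 makes no split by part.

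**The concern.** Data can be collected prospectively only while a study is approved and running. The calendar dates in 7.1 ignore this, so the label of 1b does not describe how its first weeks of data could be obtained.

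Two things follow. First, an eligible case between 1 June and approval of the amendment has no proper home. Either it is put in 1b and wrongly called prospective, or it is missed: too late for the list in 9.1.1a, and too early for prospective recording. In a series of at most 15 datasets (3.0), one lost or misplaced case matters.

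Second, several primary-endpoint events, such as water cleared from tubing, soda lime problems or manual ventilation, are counted only if someone wrote them down. Section 9.1.1a itself warns that chart access may leave the endpoint data incomplete. If cases recorded as they occur were later added to cases abstracted from old charts, one undivided proportion would depend partly on how many patients came from each part.

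**Working it through.** **1. The plan's own figures.** The protocol gives no sample size calculation and no figure for this point, so there is nothing to reproduce. The inputs are the dates in 7.1 and 15.1.

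**2. Day counts, inclusive.**
- Part 1a, 1 April to 1 June: 30 + 31 + 1 = 62 days.
- Part 1b, 1 June to 30 October: 30 + 31 + 31 + 30 + 30 = 152 days.
- Whole period, 1 April to 30 October: 213 days. Since 62 + 152 = 214, one day (1 June) is counted twice.
- Days of 1b before 1 July: 30, and 30/152 = 19.7%.
- Days of 1b from 1 July: 152 − 30 = 122. This is an upper limit on the prospective window, because the amendment must come first and its date is not given.

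These are days, not patients. They show that the label is wrong; they do not show how many cases are affected.

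**3. The windows side by side.**

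| Item | Section | Ends or begins |
|---|---|---|
| Eligibility | 3.0, 6.2, 8.1.1 (Phase 1) | ends 30 October |
| Retrospective case finding | 9.1.1a | ends 1 June |
| Part 1b, labelled prospective | 7.1 | begins 1 June |
| Commencement | 10, 15.1 | 1 July, after approvals |
| Prospective collection permitted | 9.1.1a, 9.1.1b | after an amendment, undated |

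Between the end of case finding and the amendment, patients are eligible, but no stated procedure finds them.

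**4. What combining the parts could do (assumed rates).** Let *p* be the true proportion with an event, *s_r* and *s_p* the shares of events found retrospectively and prospectively, and *k* the number of 1b patients among 15. Then

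combined proportion = *p* × [(15 − *k*) × *s_r* + *k* × *s_p*] / 15.

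The protocol gives none of *p*, *s_r*, *s_p* or *k*. With *p* = 60% and *s_p* = 100% assumed:

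| *s_r* | *k* = 0 | *k* = 5 | *k* = 15 |
|---|---|---|---|
| 50% | 30% | 40% | 60% |
| 70% | 42% | 48% | 60% |
| 90% | 54% | 56% | 60% |

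For example, with *s_r* = 50% and *k* = 5: 0.6 × (10 × 0.5 + 5 × 1.0)/15 = 0.40. Adding five 1b patients moves the figure by 2 to 10 percentage points over this range. It moves it by nothing if *k* = 0 or if detection is equal in the two parts.

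**The case against.** The strongest reply is that 1b is not active. It needs a second surge and an amendment, and the amendment is the natural place to set its methods and reporting. No patient was on an anaesthetic machine when the text was written, so the number of June cases may be zero. The analysis is descriptive, no comparison of 1a with 1b is planned, and splitting tables by part is often left to a SAP.

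Much of this stands. A reader might infer that the primary proportions do mix two ways of finding events and are therefore biased. The protocol does not support that:

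- Combining the parts is implied by the shared heading in 13.2 and the undivided endpoints in 13.1.1, but it is nowhere stated. Section 9.1.1a says that the sections after it are written for Option II, whose charts end at 1 June.
- No event-finding procedure is given for 1b. Better capture, or certain knowledge of the device used, would be an inference from the word prospective alone. Sections 6.2 and 8.1.1 point to charts and notes for the whole period.
- For 1a, Option II is a working hypothesis until charts are released. The same section still expects nursing charts and physiotherapy notes to show how patients were ventilated.

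The reply does not remove the conflict of dates, which is in the current text and is a matter for the protocol, not a SAP. Nor is an amendment certain to settle the reporting: 13.2 defers only the comparison with ITU ventilators to an amendment, and already places prospective data under the present plan.

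**Conclusion.** The window conflict holds. Part 1b cannot be prospective from 1 June; at least 30 of its 152 days must be retrospective, and more once the amendment is allowed for. Retrospective case finding stops five months short of eligibility, and 1 June belongs to both parts. This rests only on dates and conditions in the protocol.

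The effect on the primary proportions is a conditional risk. It arises only if 1b is activated, yields patients, finds events differently from 1a and is combined with it. Its size is unknown, and the percentages in the working are illustrations, not estimates. With a descriptive analysis of at most 15 datasets and no hypothesis test, the severity is minor.

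**What to change.** 1. In 7.1, define the parts by how the data were obtained. Part 1a: all eligible cases whose anaesthetic-machine ventilation began before the approval date of the prospective amendment, abstracted retrospectively. Part 1b: cases beginning on or after that date, recorded as they occur. No day is then in both parts or in neither. If no amendment is approved, 1a runs to 30 October and 1b is empty.
2. In 9.1.1a, extend the patient list and chart review from 1 June to the end of 1a.
3. Reconcile 3.0, 6.2, 7.1, 8.1.1 (Phase 1), 9.1.1a, 9.1.1b, 11 and 13.2 on whether 1b belongs to this protocol and from when.
4. In 13.2 and 13.2.2, report both primary endpoints by part, with numerators and denominators. An overall proportion may be given, but only beside the split. State that a difference between parts will not be read as a change in the safety of anaesthetic machines.

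The cost is protocol wording and one table column. The price is small denominators in each part, summing to at most 15. There is one practical limit: 9.1.1a cites a two-week quarantine of notes after ITU discharge, so charts of patients discharged after 16 October (30 − 14) would not be released within the collection period in section 11. The protocol should say how such cases are handled.
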